6.2.3. Antiplatelet Agents and Anticoagulants

Use ibrutinib with caution in subjects requiring anticoagulants or medications that inhibit platelet function. In an in vitro platelet function study, inhibitory effects of ibrutinib on collagen-induced platelet aggregation were observed. Supplements such as fish oil and vitamin E preparations should be avoided during treatment with ibrutinib. Bleeding events of any grade, including bruising and petechiae, occurred in subjects treated with ibrutinib. Ibrutinib should be held at least 3 to 7 days pre- and post-surgery depending upon the type of surgery and the risk of bleeding (see [Section 6.4](#)). Subjects with congenital bleeding diathesis have not been studied.

Subjects requiring the use of therapeutic anticoagulation therapy (e.g. Atrial fibrillation), consider the risks and benefits of continuing ibrutinib treatment. If therapeutic anticoagulation is clinically indicated, treatment with ibrutinib should be held while anticoagulation is being initiated and not be restarted until the subject is clinically stable and has no signs of bleeding. Subjects should be observed closely for signs and symptoms of bleeding. No dose reduction is required when study drug is restarted.

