5.1.1.5. Dose Modification for Cardiac Toxicity

The dose of study drug must be modified for cardiac toxicity according to the guidance in Table 3:

Table 3: Dose Modification Guidance for Cardiac Toxicity

Adverse Reaction	Occurrence	Dose Modification After Recovery Starting Dose=420mg	Dose Modification After Recovery Starting Dose=280mg	Dose Modification After Recovery Starting Dose=140mg
Grade 2 cardiac failure ¹	First	Restart at 280 mg	Restart at 140 mg	Restart at 70 mg
	Second	Restart at 140 mg	Restart at 70 mg	Discontinue Drug
	Third	Discontinue Drug	Discontinue Drug	N/A
Grade 3 cardiac arrhythmias ^{1,2}	First	Restart at 280mg	Restart at 140 mg	Restart at 70 mg
	Second	Discontinue Drug	Discontinue Drug	Discontinue Drug
Grade 3 or 4 cardiac failure Grade 4 cardiac arrhythmias	First	Discontinue Drug	Discontinue Drug	Discontinue Drug

¹Evaluate the risk-benefit before resuming ibrutinib treatment

²If clinically indicated, the use of anticoagulants or antiplatelet agents may be considered for thromboprophylaxis of atrial fibrillation.

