5.1.1.7. Dose Modification for Concomitant Use of CYP3A Inhibitors

Dose adjustment of ibrutinib secondary to concomitant use of CYP 3A4 inhibitors should follow Table 4. Concomitant use of strong CYP inhibitors is not permitted in subjects with chronic hepatic impairment.

Table 5. Dose Modification Guidance for CYP3A4 Inhibitors

Co-administered Drug	Recommended Ibrutinib Dose for the Duration of the Inhibitor Use
Mild CYP3A4 inhibitors	420 mg once daily. No dose adjustment required.
Moderate CYP3A4 inhibitors	420 mg once daily. No dose adjustment required.
Voriconazole Posaconazole at doses less than or equal to suspension 200 mg BID or delayed-release tablet 300mg QD	280 mg once daily.
Posaconazole at higher doses	140 mg once daily.
Other strong CYP3A4 inhibitors	Avoid concomitant use. If these inhibitors will be used short term (such as anti-infectives for seven days or less), interrupt IMBRUVICA.

After discontinuation of a CYP3A4 inhibitor, resume previous dose of ibrutinib.

If Bili $>$ 1.5 x ULN, avoid and/or discontinue voriconazole, posaconazole, or other strong CYP3A4 inhibitor.

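### Section 6.2.3 can be read as allowing an unreduced ibrutinib restart after Grade 3 or 4 atrial fibrillation, where Table 3 calls for a lower dose or discontinuation

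*Combined protocol and SAP*

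**What the plan says.** Section 6.2.3 (Antiplatelet Agents and Anticoagulants) opens its second paragraph: "Subjects requiring the use of therapeutic anticoagulation therapy (e.g. Atrial fibrillation), consider the risks and benefits of continuing ibrutinib treatment". If anticoagulation is indicated, "treatment with ibrutinib should be held while anticoagulation is being initiated and not be restarted until the subject is clinically stable" and free of bleeding. The paragraph ends: "No dose reduction is required when study drug is restarted". It sets no grade limit on the atrial fibrillation and does not mention Table 3.

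Section 5.1.1.5 says: "The dose of study drug must be modified for cardiac toxicity according to the guidance in Table 3". In Table 3 a first Grade 3 arrhythmia leads to a restart one level lower, and a second leads to discontinuation. The row that includes "Grade 4 cardiac arrhythmias" leads to discontinuation at the first occurrence, whatever the starting dose. Two footnotes attach to the Grade 3 arrhythmia row. Footnote 1 asks for a risk-benefit evaluation before resuming. Footnote 2 allows anticoagulants or antiplatelet agents to be considered for thromboprophylaxis in atrial fibrillation. Neither footnote mentions Section 6.2.3.

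Section 1.2.1.5 lists atrial fibrillation among the arrhythmias reported with ibrutinib, notes that some events were fatal, and sends persistent arrhythmias to the dose modification guidance in Section 5.1.1.4. In the current text that section is headed as covering non-cardiac reactions.

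**The concern.** A patient who develops Grade 3 or 4 atrial fibrillation on study and needs therapeutic anticoagulation falls under both passages. One is worded as mandatory and ends in a lower dose or in stopping. The other uses this very condition as its example and says a reduction is not needed at restart. A clinician who turns to the anticoagulation section for guidance finds what looks like a complete instruction, with nothing pointing to Table 3.

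At stake are the safety of the individual patient, for a toxicity the protocol itself describes as sometimes fatal, and consistent handling of such patients across treating clinicians. The trial has one center, so the variation would be between patients and clinicians rather than between sites.

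**Working it through.** No power, alpha or event count is involved. The check sets the two passages side by side and asks whether anything else in the protocol settles the matter.

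**Step 1: do the two passages cover the same patient?** Section 6.2.3 covers therapeutic anticoagulation, for example for atrial fibrillation of any grade. Table 3 covers arrhythmias of Grade 3 and Grade 4. Footnote 2, on the Grade 3 row, itself anticipates anticoagulation for atrial fibrillation. So they overlap for Grade 3 or 4 atrial fibrillation with anticoagulation. Exclusion criterion 9 (a requirement for anticoagulation) applies at entry and does not remove cases that arise on study.

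**Step 2: compare the instructions case by case.**

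| Case (anticoagulation started) | Section 6.2.3 | Table 3 |
|---|---|---|
| Atrial fibrillation below Grade 3 | No reduction needed at restart | No arrhythmia row, so no conflict |
| Grade 3, first occurrence | No reduction needed at restart | 420 to 280 mg, 280 to 140 mg, or 140 to 70 mg |
| Grade 3, second occurrence | No reduction needed if restarted | Discontinue |
| Grade 4, first occurrence | No reduction needed if restarted | Discontinue |
| Anticoagulation for a reason not listed in Table 3 | No reduction needed at restart | Not applicable |

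**Step 3: size of the gap if 6.2.3 is taken at face value.** For a first Grade 3 event, the ratio of the unreduced dose to the Table 3 dose is:

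- starting dose 420 mg: 420 / 280 = 1.5
- starting dose 280 mg: 280 / 140 = 2
- starting dose 140 mg: 140 / 70 = 2

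For a second Grade 3 or any Grade 4 event Table 3 allows no restart, so any restart departs from it.

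**Step 4: does anything resolve the overlap?**

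- Neither section cites the other.
- Footnote 1 to Table 3 adds a risk-benefit evaluation but does not waive the reduction.
- The tie-break in Section 5.1.1.6 applies the lower dose when an elevated bilirubin and a non-hepatic toxicity both call for a reduction. It does not cover Section 6.2.3 against Table 3.
- Section 1.2.1.5 points arrhythmias to Section 5.1.1.4, now headed non-cardiac, instead of 5.1.1.5.

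Other references show the same slippage. Section 5.1.1.6 cites Table 3 for hepatic dosing, although the hepatic table is now Table 4. Section 5.1.1.7 cites Table 4 for CYP3A dosing, although that table is now Table 5. It is an inference, not something the protocol states, that the cardiac section was added without updating the text around it.

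**The case against.** The strongest answer is that the two passages can both be obeyed. Section 6.2.3 says a reduction is not required. It does not forbid one, and it does not order a full-dose restart. It asks the clinician first to weigh whether ibrutinib should continue, and the stability and bleeding conditions are minimum conditions for a restart, not a direction to restart. The section belongs to the concomitant-medication rules and is about bleeding, so its last sentence is naturally read as saying that anticoagulation alone calls for no reduction, with the arrhythmia left to Table 3. Section 1.2.1.5, despite its outdated number, plainly sends persistent arrhythmias to the dose modification rules.

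Most of this stands. A reader might infer that the two rules are irreconcilable, or that 6.2.3 orders a restart at the same dose where Table 3 orders permanent discontinuation. The wording supports neither inference. What the objection does not remove is that the narrower meaning is nowhere stated, while atrial fibrillation is the section's own example and carries no grade limit.

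A reader might also see a parallel problem in Section 5.1.1.7: "After discontinuation of a CYP3A4 inhibitor, resume previous dose of ibrutinib". That sentence closes a section concerned only with inhibitor adjustments and is naturally read as undoing that adjustment alone. Returning a patient to a dose above a Table 3 reduction would require setting aside the mandatory wording of 5.1.1.5. For non-cardiac toxicity, Section 5.1.1.4 already allows re-escalation at the investigator's discretion after 4 weeks without recurrence. The documents do not support treating this as a second contradiction.

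Finally, a reader might infer that the safety endpoint would be distorted. That endpoint is the incidence of related adverse events of Grade 3 or higher. A triggering Grade 3 or 4 arrhythmia judged related counts whichever restart rule follows, and no further effect on the endpoint has been shown.

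**Conclusion.** The point holds as an unresolved inconsistency, limited to patients with Grade 3 or 4 atrial fibrillation who are started on therapeutic anticoagulation while on study. For them, reliance on Section 6.2.3 alone could lead to a restart at 1.5 or 2 times the Table 3 dose after a first Grade 3 event, or to a restart where Table 3 says discontinue.

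The conclusion assumes that a clinician might read the last sentence of 6.2.3 as applying to the section's own example, without consulting Table 3. The documents give no rate of Grade 3 or 4 atrial fibrillation, so the number affected among the 35 planned patients cannot be estimated and may be small. The correction is worth making because the event is a serious one and the cost is slight. No view is taken here on which dose rule is right.

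**What to change.** - Reconcile the last sentence of Section 6.2.3 with the arrhythmia rows of Table 3.
- State which passage governs when anticoagulation is started for an arrhythmia listed in Table 3, and add a cross-reference in each direction.
- Correct the reference in Section 1.2.1.5 so that arrhythmias are sent to the cardiac dose modification section.

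Which rule applies is for the sponsor's clinical and drug-safety leads to decide. The cost is one or two sentences and one corrected section number in a protocol amendment, which under Section 12.8 needs the drug company's review and approval and then IRB approval, plus a notice to the treating clinicians. No procedure, sample size or analysis changes.

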6.3. Other Systemic Immunosuppression Therapy for cGVHD

Addition of any new systemic immunosuppressant therapy (including ECP) to treat worsening cGVHD is prohibited. This will be considered a treatment failure, patient will be removed from study and treated according to institutional standard-of-care.

Any increase in the dose of methylprednisolone (or equivalent) and any resumption of treatment with methylprednisolone, after previous discontinuation, is not considered as secondary systemic therapy.

Any increase in the dose of sirolimus or calcineurin inhibitor, or resumption of treatment following discontinuation, is not considered as secondary systemic therapy, if the treatment in question was included in the immunosuppressive regimen at study initiation.

A substitution of the systemic immunosuppressant drug (e.g. tacrolimus for sirolimus) for reasons other than cGVHD progression (e.g. toxicity) may be permitted after discussion with the principal investigator and is not considered as secondary systemic therapy.

Topical therapy, including steroid creams, topical tacrolimus, oral budesonide, inhaled steroids and ophthalmic solutions are not considered as secondary therapy.

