3. STUDY DESIGN

3.1. Overview of Study Design

The rationale for the study concept is provided in [Section 1.3](#).

This is a phase II trial evaluating the safety and efficacy of the combination of Ibrutinib and Rituximab as primary treatment of cGVHD. We plan to enroll 35 patients on this study. Patients will be formally monitored monthly for 12 months to evaluate for outcome and safety endpoints. All other assessments will be done at the physician's discretion or institutional standards. All patients, responders and treatment failures, will be followed for a period of one year from the time of initiation of therapy. The primary endpoint will be the proportion of patients that are alive and off all systemic IST at 12 months following initiation of treatment.

Eligible patients will be those with a first episode of symptomatic cGVHD, requiring systemic immunosuppression for control of symptoms. Following study entry, patients will be started on:

[figure not shown]
1. Ibrutinib 420mg PO QDAY (28-day cycles) for a total of 12 cycles unless discontinued early due to toxicity (see stopping rules in section 5.1.1.4). Dose adjustments are required for patients with hepatic impairment or those receiving concomitant voriconazole or posaconazole or other strong CyP 3A4 inhibitor according to sections 5.1.1.5 and 5.1.1.6.
2. Rituximab 375mg/m² IV weekly x 4 weeks (to be started on study day 7 ± 3 days), then 375mg/m² IV q3months x 4 doses (months 4, 7, 10, 13).

Additional cGVHD treatment will include:

- **Sirolimus** (target level 4-10 ng/mL) – patients currently receiving a calcineurin inhibitor (tacrolimus or cyclosporine) and/or mycophenolate mofetil for GVHD prophylaxis will be converted to sirolimus per institutional guidelines. In the case of contraindication or intolerance to sirolimus, another systemic immunosuppressive (IS) drug (i.e. tacrolimus or cyclosporine) may be substituted at the discretion of the treating investigator.
- Short-course corticosteroids may be used, if necessary, for more rapid symptom control (≤1mg/kg Medrol, with planned taper to be completed no longer than 4 weeks).

When cGVHD manifestations have been quiescent for at least 4 weeks, sirolimus (or other IS medication) should be tapered over 4 weeks or per investigator discretion.

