8.2.2. Response Follow-up

Required testing for the response follow-up visits (months 1, 2, 3, 6, 9, 12):

- Medical history
- Physical examination, including vital signs, weight, and Karnofsky performance status
- Laboratory evaluation per institutional guidelines including CBC with differential, glucose, BUN, creatinine, total bilirubin, alkaline phosphatase, LDH, albumin, SGOT(AST), SGPT (ALT), CRP, CK, calcium, and magnesium.
- Biomarkers (correlative lab studies)
- Documentation of concomitant medications
- Completion of institutional GVHD assessment form (see Appendix E)
- Completion of a GVHD patient self-report form (see Appendix F)
- Document cumulative corticosteroid use
- Document any new systemic IST and reason for use

- Document treatment-emergent toxicities and adverse events
- Document any IVIG use
- PFTs (at 3, 6, 9 and 12 month visits only)

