9. SUBJECT COMPLETION AND WITHDRAWAL

9.1. Completion

Patients will be considered to be off study if any new systemic immunosuppressant therapy (including ECP) to treat worsening cGVHD is received. No subsequent adverse or serious adverse event reporting will be done. Further follow up off study will be according to institutional requirements.

Patients will be considered to have completed study follow up at 12 months or 30 days after the last dose of ibrutinib whichever comes last. Further off study follow up will be according to institutional requirements.

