10.2.2. Secondary Endpoints

Secondary efficacy endpoints:

To estimate:

- Chronic GVHD response (CR + PR, both individual organ response and overall response, according to 2014 NIH Response Criteria Working Group Report) – See Appendix G.
- Cumulative steroid exposure (total mg methylprednisolone or equivalent).
- Time to discontinuation of systemic immunosuppression (defined as the date that all systemic IST has been discontinued after resolution of all reversible manifestations of cGVHD. Discontinuation of immunosuppressive medications for the purpose of inducing an anti-tumor response after the development of recurrent or secondary malignancy will not be counted as successful discontinuation of IST).
- Failure-free survival (defined as being alive without the requirement for second-line cGVHD therapy). See section 6.3 for definition of second-line cGVHD therapy.
- Non-relapse and overall mortality

Safety endpoints:

To estimate:

- Incidence of grade ≥ 3 adverse events, possibly or probably related to either ibrutinib and/or rituximab.

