Appendix G. Chronic GVHD Response criteria

Organ-specific Response Criteria:

Organ	Complete Response	Partial Response	Progression
Skin	NIH Skin Score 0 after previous involvement	Decrease in NIH Skin Score by 1 or more points	Increase in NIH Skin Score by 1 or more points, except 0 to 1
Eyes	NIH Eye Score 0 after previous involvement	Decrease in NIH Eye Score by 1 or more points	Increase in NIH Eye Score by 1 or more points, except 0 to 1
Mouth	NIH Modified OMRS 0 after previous involvement	Decrease in NIH Modified OMRS of 2 or more points	Increase in NIH Modified OMRS of 2 or more points
Esophagus	NIH Esophagus Score 0 after previous involvement	Decrease in NIH Esophagus Score by 1 or more points	Increase in NIH Esophagus Score by 1 or more points, except 0 to 1
Upper GI	NIH Upper GI Score 0 after previous involvement	Decrease in NIH Upper GI Score by 1 or more points	Increase in NIH Upper GI Score by 1 or more points, except 0 to 1
Lower GI	NIH Lower GI Score 0 after previous involvement	Decrease in NIH Lower GI Score by 1 or more points	Increase in NIH Lower GI Score by 1 or more points, except from 0 to 1
Liver	Normal ALT, alkaline phosphatase, and Total bilirubin after previous elevation of 1 or more	Decrease by 50%	Increase by 2 × ULN
Lungs	- Normal %FEV1 after previous involvement - If PFTs not available, NIH Lung Symptom Score 0 after previous involvement	- Increase by 10% predicted absolute value of %FEV1 - If PFTs not available, decrease in NIH Lung Symptom Score by 1 or more points	- Decrease by 10% predicted absolute value of %FEV1 - If PFTs not available, increase in NIH Lung Symptom Score by 1 or more points, except 0 to 1
Joints and fascia	Both NIH Joint and Fascia Score 0 and P-ROM score 25 after previous involvement by at least 1 measure	Decrease in NIH Joint and Fascia Score by 1 or more points or increase in P-ROM score by 1 point for any site	Increase in NIH Joint and Fascia Score by 1 or more points or decrease in P-ROM score by 1 point for any site
Global	Clinician overall severity score 0	Clinician overall severity score decreases by 2 or more points on a 0-10 scale	Clinician overall severity score increases by 2 or more points on a 0-10 scale

ULN indicates upper limit of normal.

Source:

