1. Lee et al.. Measuring Therapeutic Response in Chronic Graft-versus-Host Disease. National Institutes of Health Consensus Development Project on Criteria for Clinical Trials in Chronic Graft-versus-Host Disease: IV. The 2014 Response Criteria Working Group Report. Biol Blood Marrow Transplant 2015; 21:984-999.

Overall Response Criteria:

Complete response (CR): defined as resolution of all manifestations in each organ or site.

Partial response (PR): defined as improvement in at least 1 organ or site without progression in any other organ or site as described above.

Overall response (OR): CR + PR

No response (NR): Defined as no response in any organ, mixed response, or progression.

Stable Disease (SD): Does not meet criteria for CR, PR or disease progression.

Organ improvement: clinically meaningful improvement defined as a decrease of 1 point or more on the 0 to 3 scale for skin, eye, mouth, esophagus, upper or lower GI tract. For joint/fascia, a clinically meaningful improvement is represented by a decrease of at least 1 point on the 0 to 3

scale or increase in the photographic range of motion by at least 1 point for any site. Liver improvement is defined as a 50% decrease in ALT, alkaline phosphatase or total bilirubin. Lung improvement is defined as an increase by 10% of the predicted absolute value of %FEV1 (eg. 50% to 60%).

Organ progression: For skin, eye, mouth, esophagus, upper or lower GI tract, a worsening of 1 point or more on the 0 to 3 scale is considered progression, except a change from 0 to 1, which is considered trivial progression since it often reflects mild, nonspecific, intermittent, self-limited symptoms and signs that do not warrant a change of therapy. For joint/fascia, a worsening of 1 point or more on the 0 to 3 scale is considered progression, even if from 0 to 1. For joints assessed by the photographic range of motion, a worsening of 1 or more points for the 7- point or 4-point scales is considered progression. Worsening of liver GVHD is defined by an increase of 2 or more times the upper limit of normal for the assay for alanine transaminase, alkaline phosphatase, or total bilirubin. For patients with lung involvement, absolute worsening of FEV1 by 10% predicted or more (eg, 50% to 40%) is considered progression.

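### Section 6.3 exempts swaps of the background immunosuppressant for any reason except cGVHD progression, so a swap made for persistent, non-progressing cGVHD is not a failure-free survival event

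*Combined protocol and SAP*

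**What the plan says.** Section 10.2.2 lists the endpoint as "Failure-free survival (defined as being alive without the requirement for second-line cGVHD therapy). See section 6.3 for definition of second-line cGVHD therapy". Section 2.2 and the synopsis make the same reference, so section 6.3 is the operative event definition as well as a rule on concomitant treatment.

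Section 6.3 treats a new systemic agent, including photopheresis, added for worsening cGVHD as treatment failure. It then lists what is not secondary therapy:

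- raising or resuming methylprednisolone;
- raising or resuming sirolimus or a calcineurin inhibitor that was in the starting regimen;
- topical treatment;
- a swap of the systemic immunosuppressant, with tacrolimus for sirolimus as the example, made for "reasons other than cGVHD progression (e.g. toxicity) may be permitted after discussion with the principal investigator and is not considered as secondary systemic therapy".

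On replacing sirolimus, section 3.1 (repeated in the synopsis) is narrower: "In the case of contraindication or intolerance to sirolimus, another systemic immunosuppressive (IS) drug (i.e. tacrolimus or cyclosporine) may be substituted".

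Appendix G treats disease that neither responds nor progresses as a category of its own: "Stable Disease (SD): Does not meet criteria for CR, PR or disease progression".

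Section 10.4 plans Kaplan-Meier estimation of the secondary survival endpoints and a log rank comparison with historical values.

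**The concern.** FFS is meant to show whether study treatment controlled cGVHD well enough that no second-line therapy was needed. A patient whose disease does not remit on sirolimus, and who is moved to another systemic drug for that reason, has arguably needed second-line therapy. If nothing has progressed, the wording of 6.3 places that patient inside the exemption and outside the rule on agents added for worsening disease. FFS would then record success where a reader would expect failure.

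The boundary matters because 6.3 already exempts steroid and baseline sirolimus or calcineurin-inhibitor increases. New or substituted drugs are therefore the main remaining sign of failure other than death. The study is open-label and at one center, and discussion with the principal investigator is the only check on a swap. A written criterion would let ambiguous swaps be classified before outcomes are known.

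**Working it through.** **Reading the texts together**

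1. The FFS event other than death is whatever 6.3 calls secondary systemic therapy (10.2.2, pointing to 6.3).
2. A swap escapes if its reason is anything except cGVHD progression. Toxicity illustrates that test and does not limit it.
3. Appendix G sets thresholds for progression, for example for skin "Increase in NIH Skin Score by 1 or more points, except 0 to 1". Disease below the threshold and without response is stable. The no-response category reads "No response (NR): Defined as no response in any organ, mixed response, or progression". It includes progression, so stable disease is the clean case.
4. A swap made for stable, persistent cGVHD therefore has a reason other than progression. It is exempt, and no other section counts it as second-line therapy.
5. Section 3.1 gives only contraindication and intolerance as grounds for replacing sirolimus. The sentence that defines the endpoint is wider than the treatment rule.
6. Discussion with the principal investigator is a procedural step. Section 6.3 attaches no criterion for inadequate response to it.

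**Direction**

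For one patient, let D be time to death, A time to an already counted second-line therapy, and S time to a swap for persistent cGVHD.

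- Current event time: min(D, A)
- Stricter event time: min(D, A, S), which is never later than min(D, A)

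With complete follow-up, 12-month FFS under the current wording is therefore equal to or higher than under the stricter one.

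**Size**

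The plan states no FFS rate, target or power, so there is no FFS figure to reproduce. Its only powered figure is the primary sample size, from section 10.3: p0 = 0.55, p1 = 0.75, one-sided alpha 0.05, power 80%.

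n = [(1.645 × √(0.55 × 0.45) + 0.842 × √(0.75 × 0.25)) / 0.20]² = 34.97, rounded up to 35.

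That reproduces, but it does not bear on FFS beyond supplying n = 35.

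If k of 35 patients have such a swap by 12 months and no other FFS event, the difference is k/35:

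| k (assumed) | Difference in 12-month FFS |
|---|---|
| 0 | 0 points |
| 1 | 2.9 points |
| 2 | 5.7 points |
| 3 | 8.6 points |
| 5 | 14.3 points |

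For example, a reported 26/35 = 74.3% becomes 25/35 = 71.4% if one swap is counted and 24/35 = 68.6% if two are.

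**Against sampling error**

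The 95% half-width is 1.96 × √(p(1 − p)/35). The last column divides it by 2.857 points per patient.

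| FFS (assumed) | Half-width | Swaps needed to move FFS by that much |
|---|---|---|
| 60% | 16.2 points | 5.7 |
| 75% | 14.3 points | 5.0 |
| 85% | 11.8 points | 4.1 |

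Half of a half-width takes about 2.1 to 2.8 swaps.

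**The case against.** The strongest reply is that tolerability swaps were plainly meant. The example in 6.3 is toxicity, section 3.1 names only contraindication and intolerance, and nothing in the protocol provides for a swap because disease persists. This stands as a reading of intent, and it is why the point is minor. It does not change what the defining sentence says.

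A second reply is that 6.3 does not cite Appendix G, so its categories are imported. That is fair, but the point does not depend on them. In ordinary usage, too, disease that persists unchanged has not progressed.

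Third, the reason for each new drug is already recorded, so a stricter FFS could be derived later. It could, but the reported endpoint would still follow 6.3 unless the rule is changed beforehand.

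Four stronger conclusions are tempting, and the documents do not support them:

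- *Every drug change is exempt.* The sentence covers only a substitution of the systemic immunosuppressant, permitted after discussion with the principal investigator. It does not cover added agents. On agents added for non-response 6.3 is silent, and no exemption covers them.
- *The historical comparison is biased in favor of the combination.* Section 1.1.2 reports no FFS for the earlier rituximab study, and no historical definition is given. If the historical figure used the same rule, the comparison is like for like, and tightening the rule only here would bias it downward.
- *FFS is inflated.* The wording permits inflation relative to a stricter definition. No such swap is documented or predicted.
- *The primary result is affected.* A patient taking a substitute immunosuppressant is still on systemic immunosuppression and does not meet the primary endpoint while taking it.

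**Conclusion.** The point holds as a gap in wording. Section 6.3, which defines the FFS event, leaves out a swap of the background immunosuppressant made for persistent, non-progressing cGVHD, and is wider than the protocol's own grounds for replacing sirolimus.

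The 2.9 points per affected patient assume 35 patients, complete follow-up to 12 months and no other FFS event in that patient. With early censoring, the Kaplan-Meier difference would no longer be exactly k/35.

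FFS is one secondary endpoint with no target rate or decision rule. The severity is minor, and the change is worth making because it is cheap.

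**What to change.** In the substitution sentence of 6.3, replace the clause giving the reason with: *for toxicity, intolerance, contraindication, drug interaction or another documented reason unrelated to cGVHD control*. State that a substitution made for inadequate cGVHD control counts as an FFS event from the start date of the new drug.

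List each substitution with its recorded reason. If the historical FFS turns out to have used the current wording of 6.3, also report FFS under that wording as a sensitivity analysis.

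Leave the rest unchanged: the planned conversion to sirolimus at entry, the rule on added agents, the other exemptions, and the removal rule. Section 9.1 keeps its own trigger ("Patients will be considered to be off study if any new systemic immunosuppressant therapy (including ECP) to treat worsening cGVHD is received"), so a patient with an FFS event of this kind is not removed from study for that reason alone.

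The cost is one reworded clause, one clarifying statement, a short listing and possibly one extra analysis. No new data are needed, because section 8.2.2 already tells sites to "Document any new systemic IST and reason for use" and to complete the GVHD assessment at months 1, 2, 3, 6, 9 and 12. Reported FFS may be slightly lower. Some judgement about the recorded reason remains, which the listing makes visible.
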